6.1.1.2. Withdrawal Period (Off Treatment)

The withdrawal period will begin with immediately after the last study dose. Study day relative to the last study dose date will be denoted as Day 0. The end of the withdrawal period is defined as the maximum of last study visit (scheduled or unscheduled) and last phone contact after the

322

last study dose. If the last study dose date is missing or ‘unconfirmed’ (eg, lost follow-up subjects), start and end days relative to the last study dose will be set as missing.

Each subject’s assessment at each visit (site or phone contact) in the withdrawal period will be assigned a study day with respect to start date of the withdrawal period (ie, the last study dose date).

- Study Day = Assessment date – the last dose date if assessment date \geq the last dose date in the extension study

6.1.1.3. Overall Study Period

Overall study period is defined as a combination of the open-label treatment period and withdrawal period. See [Table 3](#) below for summary of definition of all analysis periods and study day used for this study.

Table 3: Definition of Analysis Study Period

Analysis Study Period	Start Date	End Date	Applicable Scope
Open Label Treatment Period	Day 1*	EOT ^a	Subjects previously randomized to Placebo group
	Baseline Visit Date	EOT ^a	Subjects previously randomized to Dasotraline
Withdrawal Period	Day 0**	EOS ^b	Withdrawal Population
Overall Study Period	Day 1*	EOS ^b	Subjects previously randomized to Placebo group
	Baseline Visit Date	EOS ^b	Subjects previously randomized to Dasotraline group
Note: *: the day of the first dose of open-label study medication. ^a : Week 52 visit/ early withdrawal visit **: the day of the last dose of open-label study medication. ^b : last scheduled or unscheduled (site/phone contact) visit in withdrawal period			

Except for adverse event data, summaries and analyses of all data on OL treatment are based on the portion of study data that fall in the open-label treatment period. For adverse events, see [Section 7.4.2](#) for how a study subject is considered to be on treatment during the treatment period (ie, last study medication administration + 7 days for AE or +14 days for Serious AE).

6.1.2. Visit Windows

6.1.2.1. Visit Windows for Visits in Open-Label Treatment Period

While the Time and Events Schedule of the protocol indicates the visit timing and procedures for each visit, the timing of a subject’s actual visit timing may not be exactly as per the protocol indicated target day/visit window (note that the protocol does not indicate required visit windows, but rather provides clear guidance for visit timing). Consequently, for the purpose of analysis, the conventions outlined below will be used to allocate the data collected at each actual visit to a planned protocol visit by defining analysis visit windows.

322

The reference day is study Day 1. Definition of baseline and endpoint is provided in [Sections 6.1.3 - 6.1.4](#).

[Table 4](#) summarizes the analysis visit windows for all questionnaires, laboratory, weight, height, vital signs, ECG, physical and neurological examination, and other safety variables assessed at scheduled visits.

Table 4. Time Intervals for Analysis Visit Windows in Open-Label Treatment Period

Scheduled Visit (label on output in Extension study)	Target Day ^(a)	Time Interval (Day)
OL Baseline ^(b)	-1	<1
Week 2	14	1 – 21
Week 4	28	22 – 35
Week 8	56	36 - 70
Week 12	84	71 - 98
Week 16	112	99 - 126
Week 20	140	127 - 154
Week 24	168	155 - 182
Week 28	196	183 - 210
Week 32	224	211 - 238
Week 36	252	239 - 266
Week 40	280	267 - 294
Week 44	308	295 - 322
Week 48	336	323 - 350
Week 52	364	351 - EOT
^(a) : Relative to the day of the 1 st dose date .		
^(b) : Also refer Section 6.1.3 for details of definition of Baseline.		

If a subject has 2 or more visits in one analysis visit window (scheduled or unscheduled), the visit closest to the target day will be used as the study visit for that analysis visit window. The other additional visit(s) in the same analysis visit window will not be included in the by-visit descriptive summary analyses. However, measurements from this/these other additional visit(s) will be included in the other safety analyses (eg, Potentially Markedly Abnormal Laboratory Values or the worst case analysis) to assure all on-treatment measurements are included. If 2 study visits occur on the same number of days from the target day within the same visit window, the later one will be considered as the study visit for that target day.

Although all (scheduled and unscheduled) visits will be allocated to an analysis visit window, only planned protocol visits for each measurement will be included in the by-visit analyses. All tables and figures presenting data by visit will present only those timepoints where the applicable assessment was scheduled to be collected, unless otherwise noted below. Unscheduled and early termination data will be included for definition of endpoint or overall assessments (eg, the worst case analysis for an assessed period). Data listings will present all data, regardless of scheduled and unscheduled visits.

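### SAP Table 4 cuts Week 4 from Week 8 at Day 35/36 rather than at the midpoint, Day 42, so Week 4 visits on Days 36-42 are assigned to Week 8

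*SAP*

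**What the plan says.** SAP Section 6.1.2.1 allocates each actual visit to a planned visit by study day. A single table does this for every kind of measurement: Table 4 "summarizes the analysis visit windows for all questionnaires, laboratory, weight, height, vital signs, ECG, physical and neurological examination, and other safety variables". Week 4 has target Day 28 and window Days 22-35. Week 8 has target Day 56 and window Days 36-70. The next row reads "Week 12 84 71 - 98".

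Four further rules in the same section decide what happens to a visit after allocation:

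- With two or more visits in a window, "the visit closest to the target day will be used as the study visit for that analysis visit window". If two are equally distant, "the later one will be considered as the study visit for that target day".
- For the visit not chosen: "The other additional visit(s) in the same analysis visit window will not be included in the by-visit descriptive summary analyses". Its safety values are still kept for the worst-case and markedly abnormal value analyses.
- After allocation, "only planned protocol visits for each measurement will be included in the by-visit analyses", and tables and figures by visit "will present only those timepoints where the applicable assessment was scheduled to be collected".
- Listings show all data, and unscheduled or early termination data can still define the endpoint.

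The protocol (Table 2, Sections 11.5.2.2 and 11.5.2.3) places the Week 4 visit at Day 28 ± 3. It schedules ECG, urine drug screen and breath alcohol test at Weeks 4 and 12, but not at Week 8.

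**The concern.** Visit spacing changes from 14 to 28 days at Week 4, and the cut after Week 4 looks as if the 14-day spacing had been carried one row too far. The SAP gives no reason for treating this boundary differently.

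The visit affected matters. Week 4 is the first BE-CGI-S, EDE-Q modified and ECG after the open-label baseline. For subjects who had placebo in the core study (Pbo-Das), it is the first scheduled ECG on dasotraline, and ECG change belongs to the primary objective. At stake is whether the Week 4 column describes everyone who had a Week 4 assessment or leaves out those who came late, and whether some data from Weeks 5 to 6 are shown as Week 8.

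**Working it through.** **Inputs.** Target days and windows from SAP Table 4; selection and display rules from SAP Section 6.1.2.1; visit window and assessment schedule from Protocol Table 2 and Section 11.5.2.

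**Step 1: the boundaries.** Boundary = (earlier target + later target) / 2, with the midpoint day going to the earlier visit.

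| Pair of targets | Midpoint | Last day of earlier window, Table 4 |
|---|---|---|
| 14 / 28 | 21 | 21 |
| 28 / 56 | 42 | **35** |
| 56 / 84 | 70 | 70 |
| 84 / 112 | 98 | 98 |
| 112 / 140 | 126 | 126 |
| 140 / 168 | 154 | 154 |
| 168 / 196 | 182 | 182 |
| 196 / 224 | 210 | 210 |
| 224 / 252 | 238 | 238 |
| 252 / 280 | 266 | 266 |
| 280 / 308 | 294 | 294 |
| 308 / 336 | 322 | 322 |
| 336 / 364 | 350 | 350 |

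The midpoint reproduces 12 of the 13 boundaries exactly. The exception falls 42 − 35 = 7 days early.

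**Step 2: which days are affected.** Distances to Day 28 and to Day 56:

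- Day 36: 8 and 20
- Day 38: 10 and 18
- Day 41: 13 and 15
- Day 42: 14 and 14

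Across Days 1-364, Days 36-41 are the only days assigned to a target that is not the nearest. Day 42 is a tie, which the other 12 boundaries give to the earlier visit. So seven days, 36 to 42, would change label.

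**Step 3: a late Week 4 visit when there is also a visit on Days 43-70.** Both fall in the Week 8 window and the one closer to Day 56 is kept. Days 36-42 lie 20 to 14 days from Day 56; Days 43-70 lie at most 14 days from it. The only possible tie is Day 42 with Day 70, and the later visit wins. Of 7 × 28 = 196 day pairs, the late Week 4 visit loses all 196. It leaves the by-visit summaries, and Week 4 is empty for that subject unless another visit fell on Days 22-35.

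**Step 4: the same visit with none on Days 43-70.** Data from Day 36 to Day 42 (36/7 = 5.1 to 42/7 = 6.0 weeks) are shown as Week 8 for measures scheduled there, such as BE-CGI-S, EDE-Q modified, vital signs, weight and C-SSRS.

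**Step 5: measures not scheduled at Week 8.** An ECG, urine drug screen or breath alcohol result on Days 36-42 is allocated to Week 8, where none of the three is tabulated. It appears under no visit, whether or not the Week 8 visit took place.

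**Step 6: what is kept elsewhere.** SAP Section 6.1.5 takes QTc prolongation, ECG abnormality, vital signs and C-SSRS over the whole open-label period, so these values still count there. Effectiveness (Section 7.2.2) and drug screens (Section 7.4.3.1) are summarized by visit and endpoint, and breath alcohol (Section 7.4.8.1) by visit. None of these three has a stated worst-case summary.

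**Step 7: how late a visit must be.** The protocol window for Week 4 ends on Day 28 + 3 = 31. The first affected day is 36, which is 5 days past that limit.

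**The case against.** The SAP states no midpoint rule. The windows are complete and do not overlap, so Table 4 can be programmed as it stands. Days 22-35 are nearly symmetric about Day 28 (−6/+7), whereas Days 22-42 would be −6/+14. Table 5.1 also departs from midpoints once: for CSSA and DESS, the cut between target Days 0 and 7 is at Day 1/2. This shows that the boundary is inconsistent and unexplained rather than in breach of a written rule. It does not make the cut a good one. Where spacing changes, midpoint windows are bound to be asymmetric, as Week 2 already is (Days 1-21, −13/+7). The present cut leaves Week 8 at −20/+14; the midpoint would make it −13/+14, the same as Weeks 12 to 48.

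A reader might infer that safety data are thrown away. They are not: the loss is confined to by-visit summaries, and an abnormal ECG on Day 38 still counts in the worst-case table.

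A reader might also blame this cut for every off-schedule ECG that goes missing by visit. A Week 12 ECG taken on Day 99 falls in Week 16, where no ECG is scheduled, and is lost in the same way at a midpoint boundary. A Week 4 ECG after Day 42 would be lost under either cut.

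Finally, such late visits may be uncommon. Protocol Sections 9.2.1 and 9.4 suggest two cards of 10 capsules for a two-week interval. From an on-time Week 2 visit, 20 capsules starting on Day 15 last to Day 34. That supports a small number but does not exclude late attendance. The study is descriptive, no hypothesis is tested, and the endpoint is generally unaffected. These points limit the size of the problem and leave the inconsistency standing.

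**Conclusion.** The point holds as a minor defect in a stated rule. One of 13 boundaries is 7 days earlier than the pattern of the rest, without explanation. Followed as written, it removes a Day 36-42 visit from the by-visit summaries or labels it Week 8, and it leaves that visit's ECG, drug screen and breath alcohol results under no visit.

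The number of subjects is unknown. A reader might want to attach a head count, but the documents give no rate of late visits. Each 1% of Week 4 visits falling on Days 36-42 would be at most 0.01 × 500 = 5 subjects, and that takes all of the roughly 500 projected enrollees as reaching Week 4. The count is probably small.

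Nor should Week 4 be read as the first assessment after titration. Protocol Section 10.1.2 allows dose changes at Week 2 and throughout treatment thereafter. What the documents support is that Week 4 is the first BE-CGI-S, EDE-Q modified and ECG after the open-label baseline. It is the first scheduled ECG on dasotraline for Pbo-Das subjects only, because the others come directly from dasotraline treatment in the core study.

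**What to change.** In SAP Table 4, set Week 4 to Days 22-42 and Week 8 to Days 43-70. If the Day 35/36 cut was intended, state the reason beside the table. The change is two numbers, made before final database lock, with the matching edit in the visit-window program.

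An optional addition, separate from this correction, is to build windows from each assessment's own schedule for measures not taken at every visit (ECG, laboratory tests, drug screen, breath alcohol, SDS, SF-12, HAM-A, MADRS). That would also deal with off-schedule results at the other boundaries, at the cost of additional programming.

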6.1.2.2. Visit Window for Visits in Withdrawal Period

Visits within withdrawal period will be mapped per visit window defined in [Table 5.1](#) below for effectiveness and safety data collected in withdrawal period except of the phone contact visits used for collecting additional CSSA and DESS information.

Table 5.1: Visit Window for Clinic Visits in Withdrawal Period

Variables to be Applied	Time Interval (Day) ^a	Target Time Point (Day)	Analysis Visit (label on output)
CSSA, DESS	-5 to 1 ^(b)	0	Withdrawal Baseline
	2 – 10 ^(c)	7	Withdrawal Week 1
	11 – 17 ^(c)	14	Withdrawal Week 2
	18 – EOS ^(c)	21	Withdrawal Week 3
Other	-5 to 3	0	Withdrawal Baseline
	4 – 10	7	Withdrawal Week 1
	11 – 17	14	Withdrawal Week 2
	18 – EOS	21	Withdrawal Week 3
^a Relative to the day of the last dose of open-label study medication ^b per both phone contacts or clinic visits ^c for clinic visits only.			

If a subject has 2 or more visits in one analysis visit window, the visit closest to the targeted day will be used as the study visit for that analysis visit window. The other additional visit(s) will be denoted as unscheduled visit and not included in the by-visit descriptive summary analyses. However, measurements from this/these other additional visit(s) may be included in the other safety analyses to assure all off-treatment measurements are included. If 2 study visits occur the same number of days from the target day within the same visit window, the later one will be considered as the study visit for that target day.

Non-clinic phone contact visits within withdrawal period will be mapped per visit window defined in [Table 5.2](#) below for CSSA and DESS specifically.

Table 5.2: Visit Window for Non-Clinic/Phone Contact Visits in Withdrawal Period

Variables to be Applied	Time Interval (Day) ^a	Target Time Point (Day)	Analysis Visit (label on output)
CSSA, DESS	1 – 2	1	Day 1-2
	3 – 4	3	Day 3-4
	5 – 6	5	Day 5-6
	7 – 8	7	Day 7-8
	9 – 10	9	Day 9-10
	11 – 12	11	Day 11-12

322

	13 – 14	13	Day 13-14
	15 – 16	15	Day 15-16
	17 – 18	17	Day 17-18
	19 – 20	19	Day 19-20
	21 – 22	21	Day 21-22
	23 – 24	23	Day 23-24
	25 – EOS ^(b)	25	≥ Day 25
^a Relative to the day of the last dose of open-label study medication			
^b per phone contacts visits only.			

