6. STUDY ENDPOINTS

6.1. Safety Endpoints

The safety endpoints include:

- The incidence of overall AEs, serious AEs, and AEs or SAEs leading to discontinuation
- Clinical laboratory evaluations (serum chemistry, hematology, urinalysis)
- Clinical evaluations (vital signs including orthostatic effects, and 12-lead ECGs)
- Frequency and severity of suicidal ideation and suicidal behavior using the C-SSRS
- Change and percent change in body weight and BMI
- Change in fasting lipid panel (triglycerides, total cholesterol, high-density lipoprotein [HDL] cholesterol, and low-density lipoprotein [LDL] cholesterol)
- Change in hemoglobin A1c levels
- Change in fasting glucose levels
- Change in the symptoms of withdrawal from dasotraline from Week 52/end of treatment (EOT) as measured by
 - CSSA total score at Weeks 53, 54, and 55
 - DESS total score at Weeks 53, 54, and 55
 - HAM-A total score at Weeks 53, 54, and 55
 - MADRS total score at Weeks 53, 54, and 55

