6.1.1.1. Open-Label Treatment Period (On Treatment)

The day of the 1st dose date in the extension study will be denoted as study Day 1. All measurements at each visit will be assigned a study day relative to this date. All data collected on/after Day 1 for subjects previously randomized to placebo group in core study or on/after the extension baseline visit for subjects previously randomized to dasotraline groups and up to Week 52, including the End-of-treatment/Early Withdrawal visit, will be considered within the open-label treatment phase. That is to say, the start of the open-label treatment period is defined as Day 1 for subjects previously randomized to placebo group and the OL Baseline visit date for subjects previously randomized to dasotraline groups; the end of the open-label treatment phase is defined as the maximum of the last date of administration of study medication and the withdrawal/ completion date.

The start and end of open-label treatment period are given below:

- **Start of treatment period** =
 - = Date of the first study medication administration for subjects previously randomized to placebo group
 - = Date of the OL Baseline visit for subjects previously randomized to dasotraline;
- **End of treatment period** = maximum of the last date of administration of study medication and the withdrawal/ completion date (ie, Week 52/EOT visit date).

Each subject's assessment at each visit in pre-treatment and treatment period will be assigned a study day with respect to the first dose date in the extension study.

- Study Day = Assessment date – the first dose date in the extension study + 1; if assessment date \geq the first dose date in the extension study
- Study Day = Assessment date – the first dose date in the extension study; if assessment date < the first dose date in the extension study

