6.1.3.3. Withdrawal Baseline

See [Section 6.1.2.2](#) for the definition of Withdrawal Baseline. No imputation will be made if the Withdrawal Baseline value is missing.

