7.4.6.2. Withdrawal Period

MADRS total score, HAM-A total score, and each of the individual item scores in the withdrawal period will be summarized by presenting descriptive statistics (N, mean, median, and range) of observed values and change from DB baseline, OL baseline, and withdrawal baseline by analysis group and visit; a similar analysis will be performed by gender as well.

CSSA total score, DESS total score, and the individual scores will be summarized by presenting descriptive statistics (N, mean, median, and range) of observed values and change from withdrawal baseline by analysis group and visits based on the withdrawal population; the visits will be displayed in an order defined as follow: withdrawal Baseline, day 1-2, day 3-4, day 5-6, day 7-8, withdrawal Week 1, day 9-10, day 11-12, day 13-14, withdrawal Week 2, day 15-16, day 17-18, day 19-20, day 21-22, withdrawal Week 3. See [Section 6.1.2.2](#) for details about how to define these analysis visits per both clinic and non-clinic visits. A similar analysis will be performed by gender as well. Number and percentage of subjects with a new symptom or worsen old symptom for each DESS individual score (ie, each individual score of DESS with value of 1) by study visit and the worst case during the withdrawal period will be summarized based on the withdrawal population as well.

The number and percentage of subjects in each of the following breakdown will be summarized by study visit during the withdrawal period.

- CSSA total score: 0-7, 8-15, 16-30, 31-45, 46-60, >60;
- DESS total score category 1: 0-2, 3-5, 6-10, 11-15, 16-20;
- DESS total score category 2: 0-10, 11-20, 21-30, 31-43.

In addition, the number and percentage of subjects with change in DESS total score from withdrawal baseline by withdrawal visit and during any time point of the withdrawal period (per the worst case value) will be summarized in each of the following categories: ≤ 0 , +1, +2, +3, $\geq +4$.

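### SAP 6.1.2.2 lets one Day 1 phone call be both the CSSA/DESS withdrawal baseline and the first follow-up, and bars an end-of-treatment record from Day 2 onward as baseline

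*SAP*

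**What the plan says.** Days are counted from the last dose, which is Day 0.

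- **Baseline window (SAP 6.1.2.2, Table 5.1).** For CSSA and DESS it is Day -5 to 1, target Day 0, filled "per both phone contacts or clinic visits" (footnote b). The sentence introducing the table says that it applies "except of the phone contact visits used for collecting additional CSSA and DESS information". For other variables, including HAM-A and MADRS, the window runs to Day 3.
- **Week 1 window.** A CSSA/DESS clinic record on Day 2 to 10 is Withdrawal Week 1, target Day 7. There is no exception for the EOT visit.
- **Selection.** The record closest to target is used. On a tie, "the later one will be considered as the study visit for that target day". For the rest: "The other additional visit(s) will be denoted as unscheduled visit and not included in the by-visit descriptive summary analyses".
- **Phone windows (Table 5.2).** A call on Day 1 or 2 is the Day 1-2 time point. Nothing excludes a call already used as baseline.
- **Missing baseline (SAP 6.1.3.3).** "No imputation will be made if the Withdrawal Baseline value is missing".
- **Period (SAP 6.1.1.1).** Data up to Week 52, "including the End-of-treatment/Early Withdrawal visit, will be considered within the open-label treatment phase".
- **Use (SAP 7.4.6.2).** CSSA and DESS changes are shown by visit, with Day 1-2 directly after baseline. DESS is also tabulated by category of "change in DESS total score from withdrawal baseline by withdrawal visit and during any time point of the withdrawal period".
- **Protocol.** Section 6.1 lists as a safety endpoint "Change in the symptoms of withdrawal from dasotraline from Week 52/end of treatment (EOT) as measured by" the four scales at Weeks 53, 54 and 55. Section 15.3.2 takes as Withdrawal Baseline the last assessment up to and including the Week 52 visit. SAP Section 4 states that nothing was changed from the protocol.

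**The concern.** A baseline should be one identifiable record that is not also counted as follow-up. Here the written windows overlap on Day 1 for phone calls. A subject whose baseline is that call enters the Day 1-2 column with a change of exactly zero, and the lowest DESS change category (no increase), whatever happened clinically.

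The same rules can also set aside a value obtained on drug in favour of one obtained a day after stopping, which is not the reference that the protocol names.

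The second problem is the sharp cut at Day 1. CSSA and DESS are first collected at EOT, so there is no earlier value to fall back on. If EOT takes place on Day 2 or later and no call was made on Day 1, the subject has no CSSA/DESS baseline. The same visit on Day 2 or 3 still serves as baseline for HAM-A and MADRS. Assessment of withdrawal effects is a secondary objective, and these changes are its stated measures.

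**Working it through.** The plan gives no figure to reproduce, so the check applies the window rules to possible timings.

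**Inputs**

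- Windows, targets and tie rule: SAP 6.1.2.2.
- First call on Day 2, ±1 day, so Day 1, 2 or 3: Protocol Table 2 footnote j; SAP 5.3.2.
- EOT timing after early discontinuation: within 1 day in Protocol Table 2 footnote b, but with no limit in days in Protocol 13.2 and 14.
- Half-life 47.1 to 77.0 hours: Protocol 4.2.

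**Which record becomes baseline.** Take EOT on each day from -5 to 5 (11 days) and the first call on Day 1, 2 or 3, giving 11 × 3 = 33 timings. These are combinations, not probabilities.

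| EOT day | Call Day 1 | Call Day 2 or 3 |
|---|---|---|
| -5 to -1 | call (5) | EOT (10) |
| 0 | EOT (1) | EOT (2) |
| 1 | not separated by the rules (1) | EOT (2) |
| 2 to 5 | call (4) | none (8) |

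Totals: EOT 10 + 1 + 2 + 2 = 15; unresolved 1; Day 1 call 5 + 4 = 9; no baseline 8; sum 33. In the top row, EOT on Day -1 ties with the call and the later record wins. For Day -5 to -2 the call is simply closer.

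**Double use.** In the 9 call cases, Table 5.2 also places the call at Day 1-2, so change = x - x = 0. On the nominal schedule, calls fall on Days 2, 4, 6, 8, 10, 12, 16, 18 and 20 (9) and clinic visits on Days 7, 14 and 21 (3), giving 12 post-baseline records. Starting calls on Day 1 also gives 12 (calls on Days 1, 3, 5, 9, 11, 13, 15, 17 and 19). So 1 of 12 changes is zero by rule. The worst-case DESS category does not move because of that zero, since the lowest category already contains zero and below.

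**Displaced on-drug value.** In the 5 top-row cases the other 11 changes use a Day 1 reference. Assuming first-order decay, drug remaining at 24 hours is 0.5^(24/47.1) = 0.70 to 0.5^(24/77.0) = 0.81. Any resulting bias is probably small.

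**EOT on Day 2 or later, no Day 1 call.** The protocol's withdrawal endpoints are 4 scales × 3 weeks = 12 changes per subject. With EOT on Day 2 or 3, the 2 × 3 = 6 CSSA/DESS changes are lost and the 6 for HAM-A and MADRS remain. With EOT on Day 4 or later, the separate window for other variables also closes and all 12 are lost. An EOT record on Day 2 to 5 lies 5 to 2 days from the Week 1 target. A Week 53 visit on Day 6 to 8 lies 0 or 1 day away and is chosen, so the EOT record leaves the by-visit tables. It is labelled Week 1 only if Week 53 is missed.

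**Is that timing expected?** SAP 6.1.8 and 7.4.2 create a modified withdrawal population for subjects who do not enter the withdrawal period but whose last dose was at least 2 days before the last visit, identified in 7.4.2 as Week 52/EOT. That shows the gap was foreseen, not how often it occurs.

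**Against the protocol.** Under 15.3.2 an EOT record on Day 3 would be Withdrawal Baseline, and a call made after the Week 52 visit would not. The SAP reverses both.

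**The case against.** Several counter-arguments carry weight.

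- **The lead-in excludes phone contacts.** If it governed, the double use would disappear. But it contradicts footnote b, which is the specific rule for the baseline row. Without phone calls the no-baseline cases would rise from 8 to 4 × 3 = 12 of 33. The text needs repair either way.
- **SAP 6.1.4.2 and 7.4.1 speak of visits after the withdrawal baseline, so a baseline record should not count as one.** That is the sensible intent, but Table 5.2 and the display order in 7.4.6.2 do not carry it out. A programmer following them would fill the cell.
- **Displacement needs dosing after the EOT visit.** True, and the protocol leaves little room for it: no drug is dispensed at Week 52, and unused drug is brought to visits. A Day 1 call is also needed. After a late EOT, a Day 1 call is a reasonable baseline; it should just not be reused.
- **A Day 2 record is off drug.** This stands. The CSSA covers the preceding 24 hours, and such a reference could hide withdrawal symptoms. The Day 1 limit also matches the within-1-day request in Protocol Table 2.

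A reader might infer that subjects without a baseline vanish uncounted. The documents do not support that: SAP 7.4.6.2 reports N at Withdrawal Baseline and 7.1.2 reports the size of the withdrawal population, so the number follows by subtraction.

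**Conclusion.** The point holds as a minor defect. The Day 1 overlap is a plain rule error, producing a zero change that is not an observation. The Day 2 cut-off is a defensible choice, but it is inconsistent with SAP 6.1.1.1, with the window for HAM-A and MADRS, and with protocol 15.3.2, and it is not declared in SAP Section 4.

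A reader might go further and conclude that the withdrawal results are materially biased, or that completers in general are affected. Neither follows. A completer who takes the last dose on the morning of the EOT visit has a Day 0 record, which is the target and always wins. A discontinuer seen on Day 1 keeps a baseline. The number affected is unknown and probably small. Only descriptive CSSA/DESS change summaries are involved; observed values, score categories and DESS item summaries are unchanged, and DESS already scores only new or worsened symptoms.

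The conclusion rests on reading footnote b as governing the baseline row and on applying Table 5.2 as written. The comment on the size of bias also assumes first-order elimination.

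**What to change.** In SAP 6.1.2.2:

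1. Use the latest CSSA/DESS record on Day -5 to 0 as baseline when one exists, and a Day 1 record only otherwise. State which prevails if a clinic visit and a call both fall on Day 1; the clinic record is the natural choice.
2. Bar any record used as baseline from Table 5.2 and from all post-baseline change summaries.
3. Reconcile the Table 5.1 lead-in with footnote b, and list the departure from protocol 15.3.2 in SAP Section 4.

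In the 33 timings this restores the 5 displaced EOT values and removes all 9 double uses. The 8 timings without a baseline remain, by design. Optionally, add a flagged sensitivity summary that uses EOT records from Day 2 or 3 as reference, covering 2 × 2 = 4 of those 8, with a note that an off-drug reference may understate change.

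The cost is a few SAP sentences and programming rules, plus one small table if the option is taken. No new data and no protocol amendment are needed.
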